2.3 RISK-BENEFIT ASSESSMENT

The most common TEAEs in adult patients treated with plecanatide have been diarrhea and other gastrointestinal (GI)-related symptoms such as abdominal cramps, gas, and bloating (Investigator Brochure (IB) Ed. 9.0 for Plecanatide, 02/28/2018). It is expected that the plecanatide safety profile observed in the 6 to < 18-year old pediatric population will be similar to that observed in adult patients with CIC and IBS-C.

The amount of blood to be drawn during the course of this study (approximately 42 mL for the majority of patients, and 66 mL for patients participating in the intensive PK analysis) is not considered to be a risk to child and adolescent patients qualified for enrollment in this study.

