7. ASSESSMENT, REPORTING, RECORDING AND FOLLOW UP OF ADVERSE EVENTS

7.1 DEFINITION

An AE is any untoward medical occurrence associated with the use of a drug in humans, whether or not considered to be drug related. An AE can therefore be any unfavorable and unintended sign (including abnormal laboratory finding), symptom, or disease temporally associated with the use of an investigational product or study procedure whether or not considered related to the product or procedure.

NOTE: Specific gastrointestinal symptoms related to IBS-C are recorded daily in the electronic Diary in response to standardized questions and are BOTH efficacy AND safety response variables. These symptoms are abdominal pain, abdominal discomfort, and pain with defecation. The diary is a “real-time” patient reported outcome record that is based on “within 24 hours” patient recall. Because these symptoms are considered adequately recorded in the IBS-C Symptom Diary, they should generally not also be reported in the adverse event database that relies on a much longer patient recall period. To prevent double-recording of a single specific event, the daily IBS-C Symptom Diary record is considered the highest quality record of an event and should therefore be the only record of the same event.

All AEs, including intercurrent illnesses and regardless of the source of identification (e.g., physical examination, laboratory assessment, reported by patient), occurring during the study will be documented in the eCRF. Concomitant illnesses that existed before entry into the study will not be considered AEs unless they worsen during the treatment period.

Adverse events occurring from the time of signing the informed consent form (ICF) up to the intake of the first dose of study medication will be classified as pre-existing conditions for the study and therefore will be recorded in the Medical History page of the electronic case report form (eCRF). Serious adverse events (as defined below) occurring after the signing of informed consent but before randomization (i.e., during screening) will be collected and reported as such. A treatment emergent adverse event (TEAE) is defined as an AE that begins or worsens in frequency and/or severity after at least one dose of study drug has been administered.

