Change from baseline for a given endpoint is defined as the Study Visit value minus the Baseline Value.

Last Dose of Plecanatide

Last Dose of Plecanatide is defined as the last date that the subject received Plecanatide as determined by last date of dosing as recorded on the Study Drug Administration CRF.

Duration of Plecanatide

Duration of Plecanatide is defined as the number of days from Day 1 to the date of Last Dose of Plecanatide.

Duration on Study

Duration on study is defined as the number of days from the date of screening to the date of last follow-up visit.

Dosing Compliance

Dosing compliance will be defined by the dosing compliance ratio: the number of doses actually taken by the subject divided by the number of doses that were expected to be taken during the same period multiplied by 100.

Treatment Compliance

Treatment compliance is defined as taking equal to or greater than 80% of the drug dosage prescribed. Otherwise, the subject will be considered noncompliant with study treatment.

Rescue Medication

Dulcolax® will be provided as a rescue laxative that can be used if a subject has not had a bowel movement for at least 72 hours. Subjects will be advised that it is preferred that they do NOT take rescue medication for the period from 24 hours before to 72 hours after Day 1 of dosing.

Adverse Event

An adverse event (AE) is any untoward medical occurrence associated with the use of a drug in humans, whether or not considered to be drug related. An AE can therefore be any unfavorable and unintended sign (including abnormal laboratory finding), symptom, or disease temporally associated with the use of an investigational product or study procedure whether or not considered related to the product or procedure.

Specific gastrointestinal symptoms related to IBS-C recorded daily in the electronic Diary will be summarized separately and generally not also recorded as Adverse events.

Treatment-emergent Adverse Event

A treatment emergent adverse event (TEAE) is defined as an AE that begins or worsens in frequency and/or severity after at least one dose of study drug has been administered. Additionally, it is assumed that an Adverse Event which was reported to have started on Day 1 without an associated onset time occurred after the initiation of study drug is treatment-emergent.

Treatment-emergent Laboratory Toxicities

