9. PROPOSED TABLES, LISTINGS, AND FIGURES

9.1. **SUMMARY TABLES**

Accountability and Baseline Characteristics

14.1.1.X Subject Disposition and Termination from Study All Enrolled Subjects
– <Age Group>

14.1.2.1.X Demographic and Baseline Characteristics Safety Population
– <Age Group>

14.1.2.2.X Demographic and Baseline Characteristics FAS Population
– <Age Group>

14.1.2.3.X Demographic and Baseline Characteristics PP Population – <Age Group>

14.1.3.X Summary of 12-Lead Electrocardiograms at Screening Safety Population
– <Age Group>

14.1.4.1.X Extent of Exposure and Treatment Compliance FAS Population
– <Age Group>

14.1.4.2.X Extent of Exposure and Treatment Compliance PP Population
– <Age Group>

14.1.4.3.X Extent of Exposure and Treatment Compliance Safety Population
– <Age Group>

Efficacy

14.2.2.1.X Summary of Weekly Spontaneous Bowel Movement Rates by Study Week
FAS Population – <Age Group>

14.2.2.2.X Summary of Weekly Spontaneous Bowel Movement Rates by Study Week
PP Population – <Age Group>

14.2.3.1.1.X Summary of Weekly Average Abdominal Pain Rates by Study Week
FAS Population – <Age Group>

14.2.3.1.2.X Summary of Weekly Average Abdominal Pain Rates by Study Week
PP Population – <Age Group>

14.2.3.2.1.X Summary of Weekly Average Abdominal Discomfort Rates by Study
Week FAS Population – <Age Group>

14.2.3.2.2.X Summary of Weekly Average Abdominal Discomfort Rates by Study
Week PP Population – <Age Group>

14.2.3.3.1.X Summary of Weekly Average Abdominal Pain Scores by Study Week
FAS Population – <Age Group>

14.2.3.3.2.X Summary of Weekly Average Abdominal Pain Scores by Study Week
PP Population – <Age Group>

14.2.3.4.1.X Summary of Weekly Average Abdominal Discomfort Scores by Study
Week FAS Population – <Age Group>

14.2.3.4.2.X Summary of Weekly Average Abdominal Discomfort Scores by Study
Week PP Population – <Age Group>

14.2.4.1.1.X Summary of Weekly Bowel Movement Rates by Study Week
FAS Population – <Age Group>

14.2.4.1.2.X Summary of Weekly Bowel Movement Rates by Study Week
PP Population – <Age Group>

14.2.4.2.1.X Summary of Weekly Complete Spontaneous Bowel Movement Rates by
Study Week FAS Population – <Age Group>

14.2.4.2.2.X	Summary of Weekly Complete Spontaneous Bowel Movement Rates by Study Week PP Population – <Age Group>
14.2.5.1.X.1	Summary of Time to First Bowel Movement FAS Population – <Age Group>
14.2.5.2.X.1	Summary of Time to First Bowel Movement PP Population – <Age Group>

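### Three diary symptoms are declared safety variables and generally kept out of AE reporting, but no planned table counts, by dose, the patients in whom they worsened

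*Combined protocol and SAP*

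**What the plan says.** Protocol Section 7.1 names the symptoms: "These symptoms are abdominal pain, abdominal discomfort, and pain with defecation". It states that they "are BOTH efficacy AND safety response variables". It then directs that "they should generally not also be reported in the adverse event database", and that the diary entry "should therefore be the only record of the same event". The reasons given are the short recall period of the diary and the wish not to record one event twice.

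SAP Section 3.3.7 (Adverse Event) repeats the rule and adds a promise: symptoms "recorded daily in the electronic Diary will be summarized separately and generally not also recorded as Adverse events". It names no method, population or definition of worsening for that summary.

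Protocol Section 8.10 bases the safety evaluation on TEAEs, vital signs and laboratory data. The diary symptoms appear neither there nor among the safety endpoints in Protocol Section 2.4.3. SAP Sections 5.2.4.1 and 5.2.4.7 analyse them as secondary efficacy endpoints. A typical planned table is titled "Summary of Weekly Average Abdominal Pain Scores by Study Week" and is produced for the FAS and PP populations.

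SAP Section 3.3.4 sets missing frequencies of abdominal pain, discomfort and defecation pain to zero. A weekly severity average with no recorded scores is set to missing.

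**The concern.** Protocol Section 7.1 sets up an exchange: these symptoms mostly leave the AE database because the diary will carry the safety information. That works only if the diary data are then analysed for safety. A new or worse episode of pain after dosing would otherwise fit the protocol's own TEAE definition, and for these symptoms that information is generally routed elsewhere.

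The study is a paediatric dose-ranging trial whose primary objective covers safety as well as efficacy. Protocol Section 2.3 lists among the common adult events "gastrointestinal (GI)-related symptoms such as abdominal cramps, gas, and bloating", which lie close to the diverted symptoms. If some children get worse while the arm average improves, the reader of the final tables needs to know how many, and at which dose.

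The imputation rule adds a second problem. Protocol Section 8.4.1 describes zero as a worst case for bowel movements. For pain frequency, zero is the best possible value, so a child who worsens and leaves is scored as improved.

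**Working it through.** The plan gives no figure of its own on this point, so the check is a trace through the documents followed by three short calculations.

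**Step 1. Where the three symptoms appear in the planned output**

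| Place | Output | Population | Counts patients who worsened, by dose? |
|---|---|---|---|
| SAP 5.2.4.1 and 5.2.4.7 | Mixed-model LS mean change in rates and scores | FAS, repeated in PP | No |
| SAP 9.1, tables 14.2.3.x and 14.2.9.x | Weekly rates and scores; under SAP 5, n, mean, median, SD, minimum, maximum | FAS and PP | No |
| SAP 5.3 and tables 14.3.x | TEAEs, laboratory, vital signs, medications | Safety | No diary-symptom table |
| SAP 9.3, listings 16.2.6.1.3 and 16.2.6.2.2 | Daily entries and derived weekly values | All subjects | No, by subject |
| SAP 9.3, listing 16.2.7.3 | GI treatment-emergent events related to IBS-C | All subjects | No, by subject; source and inclusion rule not stated |

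If listing 16.2.7.3 draws on the AE page, Section 7.1 will have removed much of its content. If it draws on the diary, a rule is needed for when an entry counts as an event, and none is given.

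**Step 2. Can a favourable mean coexist with patients who worsen?**

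The documents give no SD for pain change, so these inputs are assumptions. For a normally distributed change with mean μ and SD σ, the share worsening by at least 1 point is 1 − Φ((1 − μ)/σ).

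- μ = −1, σ = 2: 1 − Φ(1) = 15.9%, or 4.8 of the planned 30 per arm.
- μ = −2, σ = 1.5: 1 − Φ(2) = 2.3%, or 0.7 of 30.
- μ = −0.5, σ = 2.5: 1 − Φ(0.6) = 27.4%, or 8.2 of 30.

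The last two are the ends of the range for μ from −0.5 to −2 and σ from 1.5 to 2.5. The minimum and maximum in the efficacy tables could reveal one extreme value, but not these counts.

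**Step 3. Effect of zero imputation on frequency**

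Take a hypothetical child with pain on b days a week at baseline and on 7 days in Week 1, with no diary entries afterwards. Weeks 2 to 4 are set to 0. The unadjusted 4-week mean change is ((7 − b) − 3b)/4.

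- b = 5: (2 − 5 − 5 − 5)/4 = −3.25 days a week
- b = 6: (1 − 6 − 6 − 6)/4 = −4.25
- b = 7: (0 − 7 − 7 − 7)/4 = −5.25

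On observed data alone, the child with b = 6 contributes +1. One such child moves the mean of a 30-patient arm by −4.25/30 = −0.14 days a week. I have taken frequency as days with pain per week; the diary scripts are not shown in the documents.

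**Step 4. Why a relative threshold will not serve**

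A 30% rise reaches the top of a 0–10 scale at 10/1.3 = 7.69, so a child with a higher baseline could never qualify. At baseline 0 a percentage rise is undefined. The baseline diary criteria in Protocol Section 3.2 set a minimum for abdominal pain only, so low or zero baselines for discomfort and defecation pain are possible.

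**The case against.** The best reply is that the symptoms are not lost. Section 7.1 gives a reasoned case for preferring the diary. The SAP promises a separate summary, lists the diary data by subject and plans listing 16.2.7.3. The efficacy tables show spread and extremes as well as means. Protocol Section 5.2.8 requires a primary reason for every withdrawal, SAP Section 5.1.1 tabulates those reasons by treatment group, and table 14.3.3.6 covers TEAEs that lead to discontinuation. The FAS label also matters little: a treated child with no post-baseline diary could not contribute to a count of observed worsening, so the main remaining difference is assigned versus received treatment.

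Most of this stands, and it rules out three stronger readings that a reader might infer.

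- That worsening can be seen nowhere. It can be found in the listings, one subject at a time.
- That the TEAE tables must show almost no abdominal pain. The rule says generally, which leaves sites discretion, and cramps, gas and bloating are not among the three diverted symptoms.
- That a child who stops because of pain is scored as pain-free throughout. This holds only for the frequency endpoints. Severity keeps the observed weeks and leaves the rest missing.

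The reply does not supply a by-dose count. A promised summary without method, population or table is not yet an analysis. Withdrawal reasons need not identify pain, and they miss children who worsen and stay. Site discretion makes the AE counts harder to interpret. The zero-imputation rule is a separate defect that a new safety table would not cure, so it needs its own change.

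**Conclusion.** The concern holds in a limited form. The SAP states an intention to summarise these symptoms separately but specifies only FAS and PP secondary-efficacy output and by-subject listings. No planned table gives, by dose, the number of patients whose abdominal pain, discomfort or defecation pain worsened. The TEAE tables will under-represent such worsening, by an amount that depends on how sites apply the rule and that cannot be calculated from the documents. The safety part of the primary objective is therefore not answered for these three symptoms.

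As to size, the 2.3% to 27.4% range in Step 2 rests wholly on assumed means and SDs. It shows that a good average can hide worsening; it does not predict a rate. The −4.25 days a week follows exactly from the SAP's rule, for a hypothetical child. Its effect on an arm mean depends on how many children leave after worsening, which the documents do not forecast. The plan should be changed, but the primary efficacy analysis is unaffected.

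**What to change.** 1. Add a Safety Population table by dose and age group, with placebo alongside. For each symptom, give the number and percentage of patients whose weekly average score rose above their own baseline by an absolute amount on the 0–10 scale, fixed before unblinding. Use observed diary days only. The placebo column is essential: weekly fluctuation will carry some patients over the threshold in every arm, and four treatment weeks give four chances. Report withdrawals attributed to these symptoms in the same table.
2. State the data source and inclusion rule for listing 16.2.7.3.
3. For the frequency of abdominal pain, discomfort and defecation pain, replace zero imputation with an observed-day rate (days with the symptom divided by days with an entry, times 7). Derive baseline in the same way and leave weeks with no entries missing, as is already done for severity. Missing weeks after withdrawal can still be informative, which is a further reason to show the withdrawals in item 1.

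The cost is one extra programmed table, one clarified listing and one changed derivation, all from data already collected. Protocol Section 8 lets the SAP supersede the protocol for analyses other than the primary one, so a SAP revision before unblinding would be enough.

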6.3 STOPPING CRITERIA

Overall safety monitoring for the trial is the responsibility of the Medical Monitor (MM) who reviews adverse event listings and provides ongoing medical oversight of adverse event reports throughout the duration of the trial. Any interruption of study drug for an individual patient, or for the study, based on the established stopping criteria outlined below will be initiated by the Medical Monitor.

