6.3.1 Individual Patient Stopping Criteria

Adverse events due to study drug that affect individual patient safety may necessitate dose interruptions or early discontinuation as described in this section.

Plecanatide therapy in adults with IBS-C and CIC has caused diarrhea in 4% and 5% of patients respectively, with severe diarrhea occurring in 0.7% and 0.6% of patients respectively. Severe diarrhea may cause dehydration. Pediatric patients may be at increased risk for diarrhea and dehydration with plecanatide therapy.

In general, study drug dosing should not be modified for mild diarrhea (Grade 1: increase of < 4 stools per day over baseline) or mild dehydration (Grade 1: dry mucous membranes, diminished skin turgor) (*National Cancer Institute, Common Terminology Criteria for Adverse Events [CTCAE] v5.0, November 27, 2017*). If study drug is not well tolerated by an individual patient, treatment will be permanently discontinued for that patient.

The following guidelines should be used in the case of moderate or severe diarrhea or dehydration:

Table 4 Individual Patient Stopping Criteria

Worst Observed Toxicity Grade NCI Common Toxicity Criteria	Dose Modification for Study Drug
Diarrhea	
Grade 2: Increase of 4-6 stools per day over baseline	No intervention required
Grade 3: Increase of ≥ 7 stools per day over baseline, incontinence, hospitalization indicated	Interrupt study drug for < 7 days until resolved to less than Grade 2 severity. If diarrhea was study drug-related, permanently discontinue study drug. If diarrhea was not study drug-related, e.g., viral gastroenteritis, then consider resuming treatment after consultation with Sponsor's Medical Monitor
Grade 4: Life-threatening consequences, urgent intervention indicated	Permanently discontinue study drug
Dehydration	
Grade 2: IV fluids indicated < 24 hour	Interrupt study drug for < 7 days until resolved to less than Grade 2 severity. If dehydration was study drug-related, permanently discontinue study drug. If dehydration was not study drug-related, consider resuming treatment after consultation with Sponsor's Medical Monitor
Grade 3: IV fluids or hospitalization indicated	Permanently discontinue study drug

Table 4 Individual Patient Stopping Criteria

Grade 4: Life-threatening consequences, urgent intervention indicated	Permanently discontinue study drug
---	------------------------------------

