6.3.2 Study Stopping Criteria

Dosing of all patients in the study will be interrupted for at least one week if ≥ 2 patients receiving study drug develop drug-related Grade 3 diarrhea and/or dehydration or if one patient develops drug-related Grade 4 diarrhea and/or dehydration. This will allow the Sponsor to assess whether the trial should be stopped or modified.

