Minor fluctuations in laboratory values for standard monitoring (abnormal values) that the investigator does not consider clinically significant or related to study drug will not be recorded as AEs. However, if the laboratory abnormality is associated with a diagnosis, then the AE term for that diagnosis will be reported.

7.2 EVENT REPORTS OF SPECIAL INTEREST – INCREASE IN BM FREQUENCY AND LOOSENING OF STOOL CONSISTENCY

An increase in the frequency of BMs and loosening of the stool consistency from baseline are expected pharmacodynamic effects of plecanatide. These same attributes (increased stool frequency and looser stool consistency) are often used to define “diarrhea”, however, in light of significant inter-patient variability in bowel habit “phenotype” and wide differences in the perception of a “normal” bowel habit there is no standard definition of “diarrhea” for this patient population. An increase in frequency or consistency for one person is a welcome event while for another patient it might be bothersome “diarrhea”. In all cases, as mentioned in the NOTE above, the frequency and consistency of each bowel movement is recorded in the electronic diary. However, this objective record often does not go far enough to characterize any change in bowel frequency or consistency as clinically important or impactful for the patient (whether beneficial or harmful).

One mechanism to introduce a level of consistency across patients, sites and the trial is to code an event as diarrhea only if it is characterized by a specific patient-reported and clinically relevant attribute such as “bothersomeness”. Therefore, for this trial, for any event associated with a significant increase from baseline in BM frequency and/or loosening of BM consistency - that would otherwise be coded as diarrhea

- the site is instructed to record it as an AE only if the patient reports that it was bothersome (as defined by each patient). Sites may question the patient/caregiver to ascertain whether or not they thought their diarrhea was bothersome.

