7.3.2 Intensity (Severity)

Investigators should assess the severity of AEs according to the following general categorical descriptors:

Mild: Asymptomatic or mild symptoms; clinical or diagnostic observations only; intervention not indicated

Moderate:	Minimal, local, or noninvasive intervention indicated; limiting age appropriate instrumental activities of daily living (ADL) (instrumental ADL includes dressing, grooming, hygiene, home skills, school skills, using the telephone, managing money, etc.)
Severe:	Medically significant but not immediately life-threatening; hospitalization or prolongation of hospitalization indicated; disabling; limiting self-care ADL (self-care ADL includes bathing, dressing and undressing, feeding self, using the toilet, taking medications, and not bedridden)

It is important to distinguish between serious and severe AEs. Severity is a measure of intensity, whereas seriousness is a regulatory definition as per **Section 7.3.1**. An AE of severe intensity may not necessarily be considered serious (by definition) or a mild AE (mild stroke) may be considered an SAE.

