7.3.3 Causality

The investigator will assess the causality/relationship between the study drug, or study procedure, and the AE and record that assessment in the eCRF.

The causal relationship of the AE to study drug will be described in terms of:

Reasonable Possibility:	There is evidence to suggest a causal relationship between the drug and the AE (e.g., the AE is uncommon and known to be strongly associated with drug exposure or is uncommon in the study population but not commonly associated with drug exposure)
No Reasonable Possibility:	There is no evidence to suggest a causal relationship between the drug and the AE

The study conduct relatedness for AEs and SAEs will also be assessed and documented. The most likely cause of an AE or SAE (e.g., disease under treatment, concomitant disease, concomitant medication, other) will be indicated in the eCRF system with details of the concomitant disease or medication or other cause.

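### Protocol 7.2 makes AE recording of increased stool frequency depend on bothersomeness, with no exception at the increase of 7 or more stools per day over baseline that Table 4 grades as 3

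*Combined protocol and SAP*

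**What the plan says.** Protocol 7.2 explains that more frequent and looser stools are the expected effect of plecanatide, that no standard definition of diarrhea exists for this population, and that the same change may please one patient and trouble another. Where such a change would count as diarrhea under usual coding, 7.2 says "the site is instructed to record it as an AE only if the patient reports that it was bothersome". Each patient defines what is bothersome. Sites are permitted, not required, to ask the patient or caregiver.

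Table 4 in 6.3.1 describes Grade 3 diarrhea as "Increase of ≥ 7 stools per day over baseline, incontinence, hospitalization indicated". The action is to interrupt study drug, and to discontinue it permanently if the diarrhea was drug-related. Under 6.3.2 all dosing is paused for at least a week "if ≥ 2 patients receiving study drug develop drug-related Grade 3 diarrhea and/or dehydration", or after one drug-related Grade 4 case. Section 6.3.2 gives no stool count of its own; it depends on Table 4.

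Section 6.3 gives the Medical Monitor responsibility for overall safety monitoring and for initiating any interruption. That person "reviews adverse event listings and provides ongoing medical oversight of adverse event reports". Under 7.3.3 the investigator will "assess the causality/relationship between the study drug, or study procedure, and the AE". In 8.10 and SAP 5.3.1, AE summaries are restricted to treatment-emergent events.

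**The concern.** The Grade 3 criterion includes an objective count, while entry to the AE data depends on perception. Where a patient meets the count and nobody calls the event bothersome, 7.2 tells the site not to record an AE, although Table 4 says study drug should be interrupted.

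This matters because diarrhea is the main expected harm of the drug and the trial compares doses in children. Section 6.3.1 itself says "Pediatric patients may be at increased risk for diarrhea and dehydration with plecanatide therapy". The study-level pause is set at two drug-related Grade 3 cases, so a single uncounted case can decide whether it is reached. By-dose TEAE tables that omit such a case would understate the effect being looked for.

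**Working it through.** There is no planned figure to reproduce. The check sets the sections side by side and then sizes the event.

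**Does any link between the count and the stopping rule work without an AE record?**

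- *Recording (7.2).* The rule covers any event otherwise coded as diarrhea, with no exception by count, grade or age.
- *Grading.* Table 4 uses the count. The general AE severity scale does not: "Investigators should assess the severity of AEs according to the following general categorical descriptors", and those descriptors (mild, moderate, severe) contain no stool number. It therefore does not restore the link.
- *Causality (7.3.3).* Both the discontinuation instruction and 6.3.2 need a drug-related judgment, and the protocol describes that judgment per AE.
- *Review (6.3).* The described inputs are AE listings and AE reports.
- *Diary during treatment.* Stool counts are captured, but the routine monitoring described in 8.6 and 5.2.6 concerns diary completion. Neither document states that counts reach the site or the Medical Monitor while the patient is on treatment.
- *Telephone contacts (5.2.3 to 5.2.5).* The scripted questions cover dosing, how the child feels, diary entry (first two calls) and concomitant medication. None asks for the number of stools.
- *Reporting.* SAP 5.2.4.2 summarizes bowel movements as weekly rates, in which a one-day rise cannot be identified. The episodic diary listing (SAP 9.3, 16.2.6.1.1.X) is an end-of-study listing.

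**How large is the event?**

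Input: exclusion 21 in Protocol 3.2 removes patients with more than 6 SBMs in either baseline week. Taking baseline as the 14-day daily mean (an assumption, since Table 4 does not define it):

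- Baseline at the entry ceiling: 6 / 7 = 0.857 per day. Threshold: 0.857 + 7 = 7.857, so 8 stools in a day.
- Zero baseline: 0 + 7 = 7 stools in a day.

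The threshold is thus about 7 to 8 stools in one day, slightly more if bowel movements after rescue laxative raise the baseline. For a patient who entered with fewer than one SBM per day this is a large change.

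**Which case remains?**

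Incontinence and hospitalization also stand under Grade 3, and incontinence is asked about daily in the diary (4.2.1). Dehydration has its own rows in Table 4 and its own place in 6.3.2, with no bothersomeness condition. The exposed case is therefore one that meets the count, is not bothersome to patient or caregiver, and has none of those three features. The documents give no rate for it.

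**The case against.** The strongest defense is that 7.2 is a reasoned and disclosed choice: stool frequency alone is a poor definition of harm for a drug meant to raise it. That stands for smaller increases. It is weaker at a count for which the protocol itself requires interruption.

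The second defense is that the stopping rules do not strictly need an AE entry. Table 4 is keyed to "Worst Observed Toxicity Grade", 6.3.2 applies when patients develop the event, and 6.3 gives the Medical Monitor overall responsibility. This also stands. A reader might infer that 7.2 disables the stopping rules, and the documents do not support that: an investigator who learns of the count can act on it. What is missing is an instruction or stated route that makes this dependable.

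Third, there are several chances to learn of the event. Parents oversee the diary at ages 6 to 11, and adolescents' entries should be discussed with a parent (SAP 3.3.7). AEs are sought by open questioning (4.3.1) and collected at the telephone contacts. Sites review rescue use at those contacts (3.3.1), and Table 2 note g adds weekly reminder calls. These are real partial safeguards, though none is stated to bring out the count.

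Four further readings go too far:

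- *That there is a long unobserved interval.* The scripted calls on Days 7 to 10 and 25 to 27 are 15 (25 − 10) to 20 (27 − 7) days apart. Section 2.1.5 reports adult severe diarrhea within the first day (IBS-C) or first 3 days (CIC), so this gap falls after the period of most concern, and the weekly calls would shorten it to about 7 days.
- *That the chance of missing the study pause can be calculated.* The adult severe-diarrhea rates in 2.1.5 and 6.3.1 (0.6% to 1.0%) are not stated to be count-based, and no document gives the share that patients would not find bothersome.
- *That all safety tables are restricted to TEAEs.* In 8.10 that restriction concerns AE summaries; laboratory tests, vital signs and medications are summarized as well.
- *That no diary alert exists.* The diary script is left to design specifications that are not public, and neither is the eCRF.

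**Conclusion.** The mismatch is present in the text: 7.2 has no exception at the one count that Table 4 grades as 3, and the described monitoring, causality and AE-table steps start from AE records. A count-only Grade 3 case could be missed by the stopping rules and the TEAE tables unless the investigator happens to learn of it.

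The size is minor. The case is probably rare, because 7 to 8 stools in a day will usually bother a previously constipated child or a parent, and its frequency cannot be estimated from the documents. Confidence is medium. The conclusion assumes that no count-based alert or recording instruction sits in the unpublished diary specifications, eCRF or site manuals. If one does, the in-trial part of the concern largely falls away, and what remains is to state it and align 7.2.

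**What to change.** 1. Add one sentence to 7.2: any increase of 7 or more stools per day over the 14-day baseline daily mean that comes to the site's attention is recorded as an AE, with its Table 4 grade and causality, whether or not it was bothersome.
2. Report by dose, in the Safety Population, the number of patients whose diary reaches that count, marking bowel movements within 24 hours after rescue bisacodyl so that laxative effects can be told apart.

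Keep the bothersomeness rule below that count and leave every threshold as it is.

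The cost is the sentence, a Table 4 grade field for these events if the eCRF lacks one, and one count from data already collected. The downsides are that a few events patients did not mind become AEs, plus slight programming work.

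The first item helps only once the site knows of the count, and the second only at the end of the study. A blinded diary flag to the site and Medical Monitor, sent only at the threshold, would close the remaining in-trial gap, but it should be optional. The check in Table 2 note h is a single pre-randomization eligibility review, so a live flag would be a new system needing validation and response procedures. It would also show a figure close to the primary endpoint to people involved in discontinuation decisions; sending it only at the threshold, with no other diary data, limits that.
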